## Enhancing the effectiveness of cognitive processing therapy among suicidal military veterans with PTSD

### 1. Objectives

Our **long-term goal** is to prevent suicides among individuals diagnosed with PTSD by integrating trauma-focused therapies with suicide-focused interventions. Consequently, the **primary objective** of this project is to test the efficacy of cognitive processing therapy (CPT), an empirically-supported psychotherapy for PTSD, when enhanced with the crisis response plan (CRP), an empirically-supported intervention for suicidal thoughts and behaviors. To accomplish these objectives, we will enroll military personnel and veterans meeting diagnostic criteria for PTSD or subthreshold PTSD (i.e., meeting threshold levels for 3 of 4 symptom criteria). We will use self-report, psychophysiological, behavioral, and ecological assessment methods to compare treatment effects. To achieve our primary objective, we specifically propose to:

#### **Aim 1: Determine if the effects of cognitive processing therapy (CPT) on suicide ideation can be enhanced by integrating the crisis response plan (CRP) into treatment**

H1: Severity of suicide ideation will be significantly reduced over time among veterans receiving CPT+CRP as compared to veterans receiving standard CPT.

H2: Among participants reporting suicide ideation at baseline, severity of suicide ideation will be significantly reduced over time in CPT+CRP as compared to standard CPT.

#### **Exploratory Aim: Determine if CPT+CRP reduces the risk of new-onset suicide ideation as compared to CPT.**

Exploratory Hypothesis: Among veterans denying active suicide ideation at baseline, rates of new-onset suicide ideation will be lower in CPT+CRP as compared to standard CPT.

### 2. Background and Rationale

Posttraumatic stress disorder (PTSD) is considered one of the “signature injuries” of the U.S. military operations in Iraq and Afghanistan (Institute of Medicine [IOM], 2012), and is the most frequently diagnosed mental health condition among veterans of these conflicts (Tanielian & Jaycox, 2008). Estimated rates of probable PTSD among veterans of Iraq and Afghanistan ranging from 5-20% (Hoge, Castro, Messer, McGurk, Cotting, & Koffman, 2004; Hoge, Terhakopian, Castro, Messer, & Engel, 2007; Milliken, Auchterlonie, & Hoge, 2007; Tanielian & Jaycox, 2008). PTSD is not just a consequence of combat, however; many military personnel and veterans experience noncombatrelated traumas such as sexual assault and domestic abuse, or have histories of early life trauma such as child abuse that can also contribute to PTSD. Regardless of the associated event, PTSD is associated with a host of functional problems and negative outcomes among military personnel including occupational and marital dissatisfaction, violence, alcohol and substance abuse, and suicide (Hoge et al., 2004; Jakupcak et al., 2007; Panagioti, Gooding, & Tarrier, 2009).

Cognitive behavioral treatments tend to be the most highly efficacious treatments for PTSD. Cognitive Processing Therapy (CPT) is one such treatment that has garnered a significant amount of empirical support, with a recent metaanalysis showing it was the most effective treatment for PTSD (Watts et al., 2013), typically yielding a 50% or larger reduction in PTSD symptoms from pre- to posttreatment (e.g., Chard, Schumm, Owens, & Cottingham; Forbes et al., 2012; Monson et al., 2006; Morland et al., 2014; Resick et al 2015; Resick et al., 2017). Recutions in PTSD symptoms are similar in magnitude when CPT is delivered in a virtual or telehealth format as compared to face-to-face delivery (Morland et al., 2011, 2014). Long-term follow-up studies conducted in nonmilitary samples also suggest the beneficial effects of CPT endure for up to 10 years posttreatment (Resick et al, 2012). However, among military samples, most studies to date have not assessed long-term effects of CPT, with the longest follow-up period among

military or veteran samples being 6 months for individual treatment (Morland et al., 2014; Resick et al., 2017) and 1 year for group treatment (Resick et al., 2015). Clinical improvement and recovery rates tend to be higher among patients who complete CPT compared to those that drop out of treatment early (Resick et al., 2008). Data also suggest that PTSD outcomes are moderated by session frequency, such that CPT sessions spaced closer together yield better effects than CPT sessions that are spaced further apart (Gutner, Suvak, Sloan, & Resick, 2016).

In addition to reducing PTSD symptoms, recent studies indicate CPT is also associated with significant short-term reduction in suicide ideation (Bryan et al., 2016; Gradus, Suvak, Wisco, Marx, & Resick, 2013; Resick et al., 2017), potentially due to its effects on PTSD and depression symptom severity (Bryan et al., 2016; Gradus et al., 2016). In several of these studies, suicide ideation increased in severity again several months after the conclusion of therapy, however, suggesting a period of increased vulnerability for suicide. Enhancing CPT with procedures that have been shown to significantly reduce suicidal thoughts and behaviors could serve to further reduce suicide risk during and after treatment completion.

One such procedure is the crisis response plan (CRP), a collaborative, patient-centered intervention that is typically handwritten on an index cards and focuses on several key components: (1) warning signs, (2) self-regulatory strategies, (3) reasons for living, (4) sources of social support, and (5) professional and crisis services. An example CRP is displayed in the figure to the right. In a randomized clinical trial previously conducted by our team, acutely suicidal patients who received a CRP showed significantly faster declines in suicide ideation and were 76% less likely to attempt suicide during the 6-month follow-up as compared to treatment as usual (Bryan et al., 2017a). Subsequent research has found that the inclusion of reasons for living section within the CRP is also associated with significant increases in positive psychological states like optimism and hope (Bryan et al., 2017b), suggesting this component may be acting upon unique mechanisms that are not influenced by other interventions.

Warning Signs: pacing feeling irritable thinking "it'll never get better"

 
• go for a walk 10 mins
 
• watch Friends episodes
 
• play with my dog
 
• think about my kids 
 
- vacation to beach in Florida
 
- Christmas Day 2012
 
 
 
• call/text my Mom or Jennifer
 
• call [name] : [contact] 
 
- leave msg w/ name, time, phone #
 
 
 
• [name]
 
• go to hospital
 
• call 911
 

### 3. Procedures

#### 3.1. Research Design

The study includes a two-arm, single blind parallel randomized clinical trial.

#### 3.2. Sample

We will enroll 750 military personnel and veterans who meet full diagnostic criteria for PTSD (i.e., having 4 of 4 symptom criteria at or above threshold levels) or subthreshold PTSD (i.e., having 3 of 4 symptom criteria at or above threshold levels), as established by the Clinician Administered PTSD Scale for DSM-5 (CAPS-5).

#### 3.3. Recruitment

Potential participants will be identified via a combination of strategies including Qualtrics Panels, video and static advertisements placed on social media pages and websites, television commercials run in select markets, and referrals from veteran support organizations and veteran-focused non-profits.

**3.3.1. Qualtrics Panels.** Qualtrics Panels is an online survey platform that maintains a database of several million U.S. residents who have volunteered to participate in periodic survey-based research. Because of their efficiency, online survey panels have been used with increased frequency to obtain general population samples for health-related and social research. Qualtrics Panels uses quota sampling methods to identify participants meeting each study's eligibility criteria. Panel members will receive an email invitation with an embedded hyperlink to webpage that includes basic information

about the study purpose, procedures, and risks and benefits, and a web-based survey that includes our screening tools. Participants who complete the screener will be financially compensated in the amount that was agreed upon with Qualtrics when they initially agreed to join a panel.

**3.3.2. Online and television advertising.** Static and video advertisements will be developed in collaboration with CBS Community Partnerships, a component of the CBS Entertainment Group, whose mission is to give back to communities across the country by capitalizing on CBS's extensive resources and long history of successful advertising and marketing initiatives, and RallyPoint, a social media platform designed by and for military personnel and veterans. Our previous collaborations with CBS Community Partnerships and RallyPoint has resulted in significantly increased enrollment across multiple research studies and clinical trials. Sample advertisements are included in this protocol, and will be updated to reflect our current affiliation with The Ohio State University. Updates and changes to these advertisements will be submitted to the IRB for review prior to fielding.

**3.3.3. Referrals from veteran support organizations and mental health professionals.** Potentially eligible military personnel and veterans will be referred to our team for screening and assessment to determine eligibility by veteran support organizations (e.g., Honor365, Project Unbreakable, the PJ Foundation, the Navy SEAL Foundation) and mental health professionals at the Department of Veterans Affairs, Department of Defense, and broader community.

**3.3.4. ResearchMatch.org.** ResearchMatch is a secure NIH sponsored volunteer registry that is available to all research team members at OSU. ResearchMatch is a free participant recruitment and feasibility analysis tool for researchers at participating institutions. The tool is offered to researchers who are conducting research which is health related.

#### **3.4. Eligibility Criteria**

Our **inclusion criteria** will include the following: (1) 18 years of age or older; (2) current or prior service in the U.S. military; (3) current diagnosis of PTSD or subthreshold PTSD; (4) ability to speak and understand the English language; and (5) ability to complete the informed consent process. Our **exclusion criteria** will include the following: (1) substance use disorder requiring medical management; (2) imminent suicide risk warranting inpatient hospitalization or suicide-focused treatment; and (3) impaired mental status that precludes the ability to provide informed consent (e.g., intoxication, psychosis, mania).

#### **3.5. Treatment Conditions**

Participants will be randomized to receive cognitive processing therapy (CPT) for PTSD with or without a crisis response plan (CRP). Both treatments will be scheduled on a daily basis during a 14-day window, and will be provided either in-person or via telehealth format, depending on the geographic location and preference of the participant.

In the **standard CPT** condition, participants will complete a self-guided safety plan, a procedure that includes personal warning signs for a suicidal crisis, self-management strategies, sources of social support, and contact information for professional resources and crisis services within the participant's local community, as well as the National Suicide Prevention Lifeline phone number. As a recommended standard care practice with suicidal patients, the combination of CPT and safety plan represents treatment as usual. The safety plan will be administered during the first therapy session.

In the **enhanced CPT** condition, participants will complete a CRP instead of a safety plan. The CRP is another recommended standard care practice with suicidal patients that includes many of the same elements as the safety plan (i.e., warning signs, self-management strategies, sources of social support, crisis services), but is created collaboratively by the patient with active input of their clinician rather than being self-guided. The CRP also includes a section focused on the participant's reasons for living, an

addition that has been shown to increase positive emotional states (e.g., hope, optimism) and lead to faster reductions in suicidal intent. The CRP will be administered during the first therapy.

The present study is therefore designed to examine if treatment effects on suicide ideation are improved with the addition of (a) active collaboration between a patient and clinician and (b) components that increase positive emotional states.

### **3.6. Clinician Training and Supervision**

Research therapists will be required to have completed the two-day CPT training workshop with follow-up consultation and supervision, as well as the one-day CRP training workshop with follow-up consultation and supervision.

### **3.7. Randomization**

Stratified block randomization with a computerized randomization algorithm will be used to assign participants to each condition. Three strata will be used: (1) suicide ideation within the past week (defined as a positive endorsement of either item 4 or item 5 on the SSI), (2) biological sex (male or female), and (3) therapy format (in-person or telehealth). Participants will be randomized in blocks of 6 and 8 to reduce the possibility of research staff being able to ascertain the randomization sequence.

### **3.8. Sample Size Estimation**

The primary outcome, suicide ideation, will be assessed up to 4 times: baseline, 2 weeks, 26 weeks, and 52 weeks). We will analyze data from the full sample and also conduct separate analyses for two subgroups of interest: those with suicide ideation at baseline and those without suicide ideation at baseline. Our primary planned analyses entail slope comparisons for suicide ideation scores.

Our assumptions for sample size estimation were based on previous research conducted by our team. In two separate pilot studies of our two-week treatment program, 50-70% of participants reported suicide ideation at baseline. We used this range to estimate the percentage of participants expected to report suicide ideation at baseline. We also based estimates on the results of a published RCT comparing the CRP to treatment as usual (Bryan et al., 2017a), which found small to moderate differences in suicide ideation between treatment groups over time ( $0.3 < d < 0.7$ ). We used this range to estimate a lower bound for the anticipated effect size (i.e.,  $d=0.3$ ).

Assuming a two-tailed  $\alpha < .05$ , a within-between interaction (i.e., treatment x time), a small correlation ( $r=0.1$ ) among repeated measures, a sample size of 112 ( $n=66$  per group) provides 80% power to detect an effect size equivalent to  $d=0.3$ . To account for expected attrition (~25%) and missing data (participants completing only 3 of 4 scheduled assessments), we will aim to enroll a total of  $N=150$  ( $n=75$  per arm) eligible participants, which provides 86% power to detect an effect size equivalent to  $d=0.3$ . Assuming two-thirds of the sample report suicide ideation at baseline—a rate comparable to our pilot studies—we will have 80% power to detect a minimum effect size of  $d=0.38$  among participants endorsing suicide ideation at baseline. Because we expect to consent and screen approximately 5 veterans to identify each eligible participant who consents to treatment, we will therefore enroll a total of 750.

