## **6. Data Analysis**

Prior to statistical analyses, we will visually inspect data to ascertain distributional properties and determine if data meet the assumptions for each of our planned analyses. Based on our previous studies, we expect the primary outcome (suicide ideation) to be positively skewed. If true for this study, we will consider and evaluate the most appropriate method for approaching each analysis (e.g., data transformations, bootstrapped confidence intervals, use of generalized linear modeling). We anticipate having up to 50% missing data from EMA and up to 30% missing data from follow-up. We will first use Little's test to determine if the missing data are ignorable (i.e., missing completely at random or missing at random). If the missing data are not ignorable, we will use multiple imputation. The number of imputed datasets will be determined based on the percent of data that are missing and contemporary recommendations. Our primary outcome for Aim 1 is suicide ideation, measured using the SSI total score.

For H1, we will use generalized linear mixed models with SSI total score as the outcome variable and treatment, time, and treatment x time entered as predictors. We will first assess change in SSI scores across the four primary time points: baseline, posttreatment, 6 months, and 12 months. H1 will be supported if there is a statistically significant treatment x time interaction indicating a faster reduction in suicide ideation among participants receiving CPT+CRP. Sensitivity analyses will then be conducted with SSI total scores from the initial screening and the eligibility interview added to the model, thereby enabling us to determine if reductions in suicide ideation coincided with the start of treatment and ruling out the possibility that observed differences between groups is attributable to pre-treatment temporal trends (e.g., participants in one group showing reductions in suicide ideation that precede the initiation of treatment).

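### Three stated figures in Sections 3.2 and 3.8 need correcting: 112 is not 66 per group, the 86% power does not reflect the 25% attrition it is said to cover, and 750 is the number screened, not the number with PTSD

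*Combined protocol and SAP*

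**What the plan says.** Section 3.8 (Sample Size Estimation) assumes a two-tailed 5% test of the treatment-by-time interaction, up to 4 assessments, a correlation of 0.1 among repeated measures and d=0.3. It makes three statements that matter here.

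- Base sample: "a sample size of 112 ( $n=66$ per group) provides 80% power".
- Inflated sample: "To account for expected attrition (~25%) and missing data (participants completing only 3 of 4 scheduled assessments"), the plan aims for 150 eligible participants, 75 per arm, "which provides 86% power to detect an effect size equivalent to" d=0.3.
- Screening: the team expects to "consent and screen approximately 5 veterans to identify each eligible participant who consents to treatment", and so "we will therefore enroll a total of 750".

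Section 3.2 (Sample) also gives 750 as the number enrolled. There it describes these people as meeting full PTSD criteria (4 of 4 symptom criteria) or subthreshold criteria (3 of 4), as established by the CAPS-5.

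Section 6 (Data Analysis) plans the main test as follows: "For H1, we will use generalized linear mixed models with SSI total score as the outcome variable", with treatment, time and their interaction as predictors.

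**The concern.** Two of the three problems can be seen without any modelling. The per-group number does not add up to its total. The two sections also differ fivefold on how many people with full or subthreshold PTSD will be enrolled.

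The third concerns the headline power. The sentence names two losses, attrition and a missed assessment, and then gives 86%. A reader will take 86% as the power left after both losses. If it is not, the plan reports more power than its own assumptions give, and anyone judging the trial's sensitivity later would start from the wrong figure.

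**Working it through.** **Inputs.** From Section 3.8: alpha 0.05, two groups, m = 4 assessments (or 3 if one is missed), r = 0.1, d = 0.3, N = 112 and 150, attrition 25%. Inferred, not stated: f = d/2 = 0.15. The support for this conversion is that it reproduces both the 80% and the 86%.

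**Formula.** Repeated-measures within-between interaction, noncentral F: λ = N·m·f²/(1 − r), df1 = m − 1, df2 = (N − 2)(m − 1).

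**Step 1. Reproduce the 80%.** N = 112, m = 4: λ = 112 × 4 × 0.0225/0.9 = 11.2, df 3 and 330, power 80.7%. N = 110 gives 79.9%, so 112 is the smallest even total that reaches 80%.

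**Step 2. Per-group number.** 2 × 66 = 132, and 112/2 = 56. Inflation for attrition gives 112/0.75 = 149.3, about the planned 150, whereas 132/0.75 = 176. The context therefore favours 56. However, N = 132 with m = 3 gives λ = 9.9, df 2 and 260, power 80.7%. The 66 could therefore be left over from a 3-assessment calculation, and only the sponsor can settle it.

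**Step 3. Reproduce the 86%.** N = 150, m = 3: λ = 150 × 3 × 0.0225/0.9 = 11.25, df 2 and 296, power 85.7%. This matches. N = 150 with m = 4 gives about 91%, which does not. With m = 4, a power of 85.5% to 86.5% needs 126 to 129 people. Since 126/150 = 0.84 and 129/150 = 0.86, that is a loss of 14% to 16%, not 25%.

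**Step 4. Apply the stated attrition.** 150 × 0.75 = 112.5, so 112 people remain if dropouts contribute nothing.

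| People analysed | Assessments each | Power |
|---|---|---|
| 150 | 3 | 85.7% |
| 112 | 4 | 80.7% |
| 112 | 3 | 73.4% |

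The first row is the basis that matches the plan's 86%. The second applies attrition only, and the third applies both losses in full.

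**Step 5. The 750.** 150 × 5 = 750, so in Section 3.8 it is the number consented and screened. In Section 3.2 it is the number meeting diagnostic criteria. Section 3.8 uses the verb enroll for both 150 and 750, which is probably how the two were merged.

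**The case against.** **The basis of the 86% can be found.** The sentence itself mentions 3 of 4 assessments, and 150 people at 3 assessments reproduces the figure. That is right, and it would be too strong to say that the plan gives no basis. What the text leaves out is that all 150 are counted.

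**One 25% loss may be expressed in two ways.** 150 × 3 = 450 observations, the same as 112.5 × 4. This reading is possible, but the sentence lists attrition and missing data as two separate allowances, so it is not the natural one.

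**The planned analysis is a mixed model, which keeps partial data.** This stands. Someone who leaves after week 2 still contributes, so the true loss of power would be smaller than in Step 4. How much smaller depends on when people drop out, which the documents do not give. Section 3.8 also speaks of slope comparisons, whereas the calculation that reproduces the plan is an overall interaction test. For these reasons I give no mixed-model power range. The Step 4 figures hold only if dropouts contribute no data.

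**The 750 is explained within Section 3.8.** This is also right: the last sentence makes the meaning recoverable. The conflict over diagnostic status lies between Sections 3.2 and 3.8.

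**Conclusion.** The point holds for three figures.

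1. The per-group number is inconsistent with its total whatever is assumed: 66 printed, against 56 for a total of 112.
2. The two sections disagree on enrolment of people meeting criteria: 750 against 150. This needs no assumption either.
3. The 86% is mislabelled. On r = 0.1 and the inferred f = 0.15, it allows for the missed assessment but removes no one for attrition. The same calculation with 25% contributing no data gives 80.7% (4 assessments) or 73.4% (3).

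A reader might go further in three ways that the documents do not support.

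- *The trial is too small.* It is not shown to be. The 150 is the attrition-inflated 112, and the 80% target is met if those retained complete all 4 assessments. The 73.4% needs every dropout to contribute nothing and everyone else to miss a visit.
- *The subgroup figure is wrong.* Section 3.8 says, "Assuming two-thirds of the sample report suicide ideation at baseline", "we will have 80% power to detect a minimum effect size of" d=0.38. Two-thirds of 150 is 100 people, and 100 people at 2 assessments reproduces 0.38. So do about 82 at 3 assessments and 70 at 4. The basis is not stated, but no error is shown.
- *The effect size is misused because d is not defined for the interaction test.* That argument rests wholly on the inferred f = d/2. It points to missing detail and does not show a fault.

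**What to change.** Three changes of wording in the combined protocol and SAP:

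1. **Section 3.8, base sample.** Correct or confirm the per-group number: 56 if the total is 112. If 66 was intended, the total and its inflation to 150 have to be reconciled with it.
2. **Section 3.8, power of N=150.** Label the 86% as all 150 analysed at 3 assessments. Beside it, give the figure net of 25% attrition: about 81% with 4 assessments and 73% with 3, if dropouts contribute no data. Add that a mixed model using partial data would lose less.
3. **Section 3.2.** State 150 eligible participants (full or subthreshold PTSD) randomised from about 750 consented and screened, and keep the verb enroll for one of the two numbers only.

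The cost is protocol wording, with no added participants, visits or data. The stated power will read less favourably than a bare 86%.
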